#### *Exploratory Efficacy Endpoints:*

The primary efficacy endpoint will be change in percent BV5 measured by computed tomography from baseline to day 28 after treatment initiation.

The secondary efficacy endpoints will be as follows:

1. Change in percent BV5-10 measured by computed tomography from baseline to day 28 after treatment initiation.
2. Change in percent BV10 measured by computed tomography from baseline to day 28 after treatment initiation.
3. Change in percent BV5 measured by computed tomography from baseline to day 90 after treatment initiation.
4. Change in percent BV5-10 measured by computed tomography from baseline to day 90 after treatment initiation.
5. Change in percent BV10 measured by computed tomography from baseline to day 90 after treatment initiation.
6. Airway (siVaw) and lobar (iVLobe) Volumes at end-inspiration (TLC).

#### *Images and Analyses:*

Functional Respiratory Imaging (FRI) analysis for pulmonary vascular segmentation and lobar volumes will be carried out by Fluidda.

***Sample Size and Power:***

This sub-study will include up to 60 subjects randomized to either Acebilustat or matched placebo. Given the sub-study nature of this protocol, enrollment and ratio of active treatment to placebo will be determined by 1) randomization at the level of primary protocol (COVID-19 COPPS), 2) COPPS Acebilustat sub-study enrollment, and 3) success of CT-sub-study recruitment itself.

Power calculations were performed to evaluate the power of the sub-study under a range of assumptions. These calculations are based on a two-sided t-test comparing the change from baseline between the acebilustat and placebo arms. In all calculations, a total sample size of 60 and a Type I error of 0.05 were assumed.

| Power | N - ace | N - placebo | $\delta$ |
|-------|---------|-------------|----------|
| 0.76  | 30      | 30          | 0.7      |
| 0.86  | 30      | 30          | 0.8      |
| 0.93  | 30      | 30          | 0.9      |
| 0.97  | 30      | 30          | 1        |
|       |         |             |          |
| 0.75  | 35      | 25          | 0.7      |
| 0.85  | 35      | 25          | 0.8      |
| 0.92  | 35      | 25          | 0.9      |
| 0.96  | 35      | 25          | 1        |
|       |         |             |          |
| 0.71  | 40      | 20          | 0.7      |
| 0.82  | 40      | 20          | 0.8      |
| 0.90  | 40      | 20          | 0.9      |
| 0.95  | 40      | 20          | 1        |

The assumptions varied were 1) the randomization ratio (1:1, 1.4:1, and 2:1) and 2) the effect size ( $\delta = 0.7, 0.8, 0.9, 1$ ). The effect size is defined as the difference between the two arms divided by the standard deviation.  $\delta = 1$  corresponds to a difference between the two arms that is equal to 1 standard deviation.  $\delta = 0.7$  corresponds to a difference of 0.7 standard deviations between the two arms. The table above shows the power under the various settings. We are well-powered to observe differences of  $\delta = 0.8$  or larger under any of the randomization ratios.

***Statistical Analyses:***

The primary efficacy analysis of change in percent BV5 from baseline to day 28 and 90 will be performed on the intention-to-treat (ITT) population. We will fit a linear mixed effects model regressing the day 28 and 90 changes in percent BV5 from baseline on

treatment arm. The model will additionally include fixed effects for visit, a visit by treatment interaction, and lobe. To address our primary hypothesis, we will test whether the coefficient corresponding to a treatment effect at day 28 is non-zero. A random intercept for lobe and participant will be included to account for the correlation induced by repeated measures within a participant. An unstructured variance-covariance matrix will be assumed. If this model fit fails to converge, a compound symmetry covariance structure will be considered to model correlation. If necessary, a per-scan composite from across all lobes may be formed in order to conduct analyses at the participant rather than the lobe level. For clinical outcomes, a similar approach will be taken, excluding the lobar component. Secondary analyses will repeat the primary analysis for the following outcomes: change in percent BV5, percent BV5-10, percent B10 from baseline to days 28 and 90. Additional secondary analyses will consider the change observed in each lobe and the maximum observed change in any lobe.

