#### *Criteria for Evaluation:*

All patients enrolled into the parent COVID-19 COPPS Acebilustat protocol will be eligible to participate on a voluntary basis under a separate Informed Consent Form. Airway, Lobular and Pulmonary Blood Vascular volumes (BVx), and proportional blood volume distribution (percent total for each BVx) will be assessed at baseline (Day 0-3) and at the end of treatment (Day 28), and during long-term follow up (Day 90) using a standardized chest computed tomography protocol. Changes in BVx across 3 compartments [ $<5$  mm cross sectional area (BV5), 5-10 mm cross sectional area (BV5-10), and  $>10$  mm cross sectional area (BV10)] will be assessed over the total duration of the study compared across intervention vs placebo arms.

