| Oropharyngeal swab                                | X                                  |          |          |          | X              |          |          |          |          |                 |           |           | X               |                 |                 |                  |                  |                  |
| Blood collected by phlebotomy for clinical labs   | X                                  |          |          |          | X              |          |          |          |          |                 |           |           | X               |                 |                 |                  |                  |                  |
| Blood collected by phlebotomy for biobanking      | X                      |          |          |          |                |          |          |          |          |                 |           |           | X   |                 |                 |                  |                  |                  |
| Telehealth visit                                  |                                    |          |          |          |                |          |          |          |          | X               |           |           |                 | X               |                 | X                | X                | X    |
| CT Imaging  | I                      |          |          |          |                |          |          |          |          |                 |           |           | I   |                 | I   |                  |                  |                  |
| Administration of drug - Acebilustat sub-protocol | Every day from days 1-28 inclusive |          |          |          |                |          |          |          |          |                 |           |           |                 |                 |                 |                  |                  |                  |

2- Denotes additional telehealth visit if needed for following any ongoing AEs.

3- Imaging visit window: the baseline scan should occur up to and including Day 3 while on trial. D28 and D90 have a window of ±3 Days. Women of childbearing potential are required to complete a pregnancy test prior to their Baseline, Day 28, and Day 90 scans.

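### The primary model for change in percent BV5 omits baseline percent BV5; adding it would generally gain precision at no data cost

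*Combined protocol and SAP*

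**What the plan says.** All references are to the CT Imaging Substudy in section 3 of the combined protocol and SAP.

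- **Exploratory Efficacy Endpoints.** Despite that heading, one endpoint is named primary: "The primary efficacy endpoint will be change in percent BV5 measured by computed tomography from baseline to day 28 after treatment initiation".
- **Statistical Analyses.** The day 28 and day 90 changes are regressed on arm. "The model will additionally include fixed effects for visit, a visit by treatment interaction, and lobe". There are random intercepts for lobe and participant. For the primary hypothesis, "we will test whether the coefficient corresponding to a treatment effect at day 28 is non-zero". The fallbacks are a compound symmetry covariance and a composite per scan.
- **Statistical Analyses, secondary.** "Secondary analyses will repeat the primary analysis for the following outcomes" (percent BV5, BV5-10 and BV10 at both visits). "Additional secondary analyses will consider the change observed in each lobe and the maximum observed change in any lobe".
- **Sample Size and Power.** "These calculations are based on a two-sided t-test comparing the change from baseline between the acebilustat and placebo arms". Total N is 60, alpha is 0.05, and the section claims good power for effects of 0.8 SD or more.

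Baseline percent BV5 is not a model term in any of these places or elsewhere in the supplied text.

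**The concern.** Every participant who has a change score also has a baseline value, so the covariate is available without further data. Nothing already in the model does its work. The response is a change score, so the participant intercept does not adjust for baseline. The lobe effect absorbs mean differences between lobes, not baseline differences between participants.

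Leaving baseline out forces the slope of follow-up on baseline to 1. With a smaller true slope, the unadjusted estimate over-corrects: an arm that starts higher by chance appears to improve less. This averages out over repeated randomisations, but it widens the interval and can move the estimate in the one trial that is run.

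The sub-study has at most 60 participants, and the realised allocation depends on voluntary recruitment. The plan's own power at 0.7 SD is 0.71 to 0.76, below 0.80 in all three allocations.

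**Working it through.** **Inputs from the plan (Sample Size and Power).** N = 60 split 30/30, 35/25 or 40/20; two-sided alpha 0.05; effect δ in units of the SD of change.

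**Inputs assumed.** The correlation ρ between baseline and day 28, and k = SD(day 28)/SD(baseline). The documents give neither. All figures are per participant, the level of the plan's t-test.

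**1. Reproduce the plan's powers.** Noncentral t with 58 df and noncentrality δ/√(1/n₁ + 1/n₂). At 30/30 and δ = 0.8 this is 0.8/0.2582 = 3.098, giving power 0.861 (plan: 0.86). At 35/25 and 40/20 it gives 0.852 and 0.819 (plan: 0.85 and 0.82). All 12 cells agree.

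**2. Variance ratio, adjusted to unadjusted.** In units of the baseline variance, the change has variance 1 + k² − 2ρk, and the residual after adjustment has variance k²(1 − ρ²). The ratio is

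VR = k²(1 − ρ²)/(1 + k² − 2ρk), which is (1 + ρ)/2 at k = 1.

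| k | ρ = 0.5 | ρ = 0.7 | ρ = 0.9 |
|---|---|---|---|
| 0.7 | 0.47 | 0.49 | 0.40 |
| 1.0 | 0.75 | 0.85 | 0.95 |
| 1.15 | 0.85 | 0.95 | 0.995 |
| 1.3 | 0.91 | 0.99 | 0.92 |

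The gain vanishes where the slope ρk is close to 1.

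**3. Power with adjustment, k = 1.** Noncentral t with 57 df and noncentrality δ/√[VR(1/n₁ + 1/n₂)(1 + 1/56)]; the last factor is the price of estimating the slope. At 30/30, δ = 0.8 and ρ = 0.5: 0.8/√(0.75 × 0.06667 × 1.0179) = 3.546, giving 0.94.

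| Allocation | δ | Unadjusted | ρ = 0.5 | ρ = 0.7 | ρ = 0.9 |
|---|---|---|---|---|---|
| 30/30 | 0.7 | 0.76 | 0.86 | 0.82 | 0.77 |
| 35/25 | 0.7 | 0.75 | 0.85 | 0.81 | 0.76 |
| 40/20 | 0.7 | 0.71 | 0.82 | 0.77 | 0.72 |
| 30/30 | 0.8 | 0.86 | 0.94 | 0.91 | 0.87 |
| 35/25 | 0.8 | 0.85 | 0.93 | 0.90 | 0.86 |
| 40/20 | 0.8 | 0.82 | 0.91 | 0.87 | 0.83 |

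A simulation of 20,000 trials per cell agreed with the formula within 0.005 in all 18 adjusted cells. The adjusted test's type I error was 0.048 to 0.052.

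**4. Interval width and detectable difference, 30/30, k = 1.** The 95% half-width goes from 2.002 × 0.2582 = 0.52 to 0.45/0.48/0.51 SD of change. The difference detectable with 80% power goes from 0.74 to 0.64/0.68/0.72.

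**5. Worst case.** With VR = 1 (slope exactly 1), the largest power loss over the plan's grid is 0.0079, at 40/20 and δ = 0.7.

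**6. Chance imbalance, if baseline scans precede dosing.** P(|difference| > 0.3 SD) = 2[1 − Φ(0.3/√(1/n₁ + 1/n₂))] = 0.245, 0.252 and 0.273 for the three allocations. A 0.3 SD difference moves the unadjusted estimate by |1 − ρk| × 0.3/√(1 + k² − 2ρk). At k = 1 that is 0.15/0.12/0.07 SD of change, or 19%/15%/8% of δ = 0.8.

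**7. Carry-over to lobes.** With 60 participants, an assumed five lobes, two visits, complete data and exchangeable lobes, the generalised least squares day-28 effect equalled the difference in participant mean change in three of three data sets. It did not with a lobe-specific covariance (0.029 against 0.001). So the variance and shift results apply to an equal-weight mean of lobes. The standard error, power and type I error of the planned lobe-level model do not follow from them.

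**The case against.** The case against acting is that nothing here is an error. The unadjusted change-score model matches the stated endpoint and the test that was powered. The endpoints are headed exploratory. The power claim covers only 0.8 SD or more, where every cell is already at least 0.82. The gain rests on unknown ρ and k and can be nil or slightly negative: at k = 1.15, ρ = 0.9 and at k = 1.3, ρ = 0.7, power at 30/30 and δ = 0.8 falls from 0.861 to 0.857 and 0.858. The figures are per participant, while the planned model is per lobe. A general adjustment rule may exist in the master protocol, which was not supplied.

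Much of this stands. The point is one of efficiency and robustness, and its size for percent BV5 cannot be read from the documents. It is also fair that lost precision and the imbalance shift are one effect seen two ways, on average and given the realised baseline difference; they must not be added together.

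It does not outweigh the recommendation. Exploratory or not, the endpoint is named primary, tested and powered. The possible loss is under one percentage point, against up to about 11 points in the equal-SD range (0.71 to 0.82 at 40/20). If the master protocol does hold a rule, the sub-protocol should cite it.

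One further caution is sound. Under Criteria for Evaluation and footnote 3 of the schedule of assessments, "the baseline scan should occur up to and including Day 3 while on trial", while drug is given from day 1. A baseline difference in later scans may therefore include drug effect. This already affects the planned change score. If treatment shifts the baseline scan by s, the change score loses all of s and the adjusted estimate loses slope × s. With s = 0.2 and a true effect of 0.5 baseline SD, simulation gave 0.30 for the change score and 0.40/0.36/0.32 adjusted at ρ = 0.5/0.7/0.9. Adjustment does not worsen the problem for slopes between 0 and 1, but does not cure it.

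**Conclusion.** The concern holds as a recommended improvement. The model has no baseline percent BV5 term in its primary form, its fallbacks or its secondary analyses. The omission does not by itself invalidate the test; that was checked for a participant-level day-28 comparison only, and the type I error of the lobe-level model was not examined. With equal SDs and ρ from 0.5 to 0.9, adjustment lowers the variance by 25% to 5% and raises power at 0.7 and 0.8 SD by about 11 points down to about 1. Other SD ratios widen that range in both directions. The direction is secure unless the true slope is close to 1, where the cost is negligible.

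**What to change.** Before unblinding, amend Statistical Analyses as follows.

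- **Primary model.** Add baseline percent BV5 and its interaction with visit as fixed effects. If analysed per participant, use the composite baseline. If analysed per lobe, use the lobe's own baseline and the participant's mean baseline, each with its visit interaction.
- **Secondary models.** Use the matching baseline for percent BV5-10 and percent BV10, and the lobe's own baseline in the per-lobe analyses. For the maximum change in any lobe, use the participant's composite baseline, because that lobe is chosen after its change is seen.
- **Sensitivity analysis.** Retain the present unadjusted model.
- **Avoid** a model that constrains the arms to equal baseline means, because some baseline scans may follow the first dose. The timing of the baseline scan needs separate attention.

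The cost is two model terms per participant, or four in the per-lobe version. No new scan, visit or data item is needed, and the power table can stand as the unadjusted calculation.

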#### *Sub Study Design:*

Enrollment for this CT imaging sub-study will parallel that of the parent Acebilustat subprotocol of the COPPS master protocol. The sub-study will enroll symptomatic patients who have consented for the primary clinical study and who additionally volunteer and consent to participate in the CT imaging sub-study. The CT imaging sub-study is designed to compare up to 60 total patients including both Acebilustat and

placebo treated patients, according to level of voluntary participation and the outcome of randomization to the Acebilustat subprotocol within the COPPS master. Imaging will be performed at baseline (within 72 hours from enrollment), at day 28 (end of treatment), and day 90 (long-term follow-up). All parent study inclusion and exclusion criteria apply. The only additional inclusion criterion is voluntary consent to participate in this CT imaging sub-study. There are no further additional exclusion criteria that pertain to this sub-study.

When a subject consents to participate in the study with CT imaging, the following actions will be performed during relevant study visit:

- Schedule appropriate CT times with radiology for baseline, day 28, day 90 scans.
- Explain the study procedure and practice the breathing patterns with the subject.
- Conduct the HRCT scans at end-inspiratory breath hold.

Actions to be performed after the study visit:

- Send the CT images and relevant reports to Fluidda for FRI analysis.

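### The CT sub-study's lobe-level primary model does not define its covariance, and some ways of fitting it leave part of the shared scan variance out of the Day-28 standard error

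*Combined protocol and SAP*

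**What the plan says.** Section 3, CT Imaging Substudy, Statistical Analyses, regresses the Day-28 and Day-90 changes in percent BV5 on arm, visit, their interaction and lobe. The primary test is the arm effect at Day 28. On correlation the section gives three statements:

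- The random effects are limited to two intercepts: "A random intercept for lobe and participant will be included to account for the correlation induced by repeated measures within a participant".
- The covariance gets a single short sentence: "An unstructured variance-covariance matrix will be assumed".
- A fallback is then offered in case of non-convergence: "If this model fit fails to converge, a compound symmetry covariance structure will be considered to model correlation".

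No participant-by-visit (scan) effect is named, and neither is a degrees-of-freedom method. The unit spanned by the unstructured matrix, or by its fallback, is not stated. A participant-level alternative is optional: "If necessary, a per-scan composite from across all lobes may be formed". It has no trigger and no formula. The section adds: "For clinical outcomes, a similar approach will be taken, excluding the lobar component".

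Sample Size and Power works with one value per participant: "These calculations are based on a two-sided t-test comparing the change from baseline between the acebilustat and placebo arms". The endpoints stand under the heading "Exploratory Efficacy Endpoints", and Sub Study Design describes a voluntary comparison "designed to compare up to 60 total patients".

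**The concern.** Under Monitoring the breathing signal, each visit yields one breath-hold image, so all lobe values at a visit share whatever is peculiar to that scan. Participants who recover at different rates would produce the same pattern. A participant intercept carries only what is constant across Day 28 and Day 90. A lobe intercept carries only what is constant within a lobe. Variance shared by the lobes of one scan, but specific to its visit, has no term of its own. Part of it then goes to the residual, where averaging over lobes wrongly shrinks it.

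Two analysts following the text could therefore fit different models and report different p-values for the sub-study's one primary test. Some of those models give Day-28 intervals that are too narrow.

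**Working it through.** **The plan's own figure.** For 30 per arm and an effect of 0.8 SD, the noncentrality is 0.8/√(1/30 + 1/30) = 3.098. With 58 df and two-sided 0.05 the power is 0.8614, against 0.86 in the table. All 12 table entries reproduce to rounding. The table rests on a participant-level t-test and is not in question.

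**Assumptions, none of them in the documents.** There are five lobes. Variances are sp (participant), sl (lobe within participant), ss (scan, that is participant by visit) and se (residual). The variance of a participant's mean Day-28 change is set to 1. The lobe-specific part of it is (sl + se)/5 = 0.2, with sl = se = 0.5. Then ss = p, the scan share, and sp = 0.8 − p. Visit variances are equal and data complete unless stated.

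**True Day-28 variance per participant:** sp + ss + sl/5 + se/5.

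**Intercepts only.**
- Per participant, the residual pools 1 df with expectation 5ss + se and 4 df with expectation se, giving se + ss.
- Matching the other strata gives a lobe component of sl − ss/2 and a participant component of sp + ss/2.
- Modelled variance: sp + ss/2 + (sl − ss/2 + se + ss)/5 = sp + 0.6ss + sl/5 + se/5.
- The part lost is (L − 1)/(2L) = 4/10 = 40% of ss. The ratio of modelled to true variance is 1 − 0.4p.

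**Unstructured visits within each lobe, plus the participant intercept.** With equal visit variances the result is the same.

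**Compound symmetry over all ten records.**
- Of the 45 pairs of records, 20 share a scan and 5 share a lobe, so the common covariance is sp + (20/45)ss + (5/45)sl.
- Modelled variance: sp + 0.556ss + 0.289sl + se/5.
- The standard error is too small only if ss exceeds about one-fifth of sl.
- If the lobe intercept is read as shared across participants, it duplicates the fixed lobe effect and the intercepts-only model reduces to this one.

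**Large-sample size, 2·[1 − Φ(1.96·√ratio)]:**

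| Scan share p | Intercepts only, or visits within lobe: ratio | Size | Compound symmetry: ratio | Size |
|---|---|---|---|---|
| 10% | 0.96 | 5.5% | 1.00 | 5.0% |
| 30% | 0.88 | 6.6% | 0.911 | 6.1% |
| 50% | 0.80 | 8.0% | 0.822 | 7.6% |

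At p = 20% the ratio is 0.92 and the size 6.0%, an excess of about 1 point. The scale matters. A scan share of 20% of single-lobe variance, with components 0.3, 0.2, 0.2 and 0.3 for participant, lobe, scan and residual, is 0.2/(0.3 + 0.2 + 0.04 + 0.06) = 33% on the scale used here, and gives 6.7%.

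**Simulation at 30/30 with a t cut-off on 58 df,** at p = 10, 30 and 50%: intercepts only 5.5, 6.6 and 7.6%; visits within lobe 5.7, 6.3 and 8.4%; compound symmetry 4.9, 6.0 and 7.2%. A t-test on the per-scan mean gives 4.8 to 5.1%.

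**Readings that keep the scan variance.**
- An unstructured 2x2 over visits at participant level has size 5.0% in every scenario run.
- A full matrix over all ten records also keeps it, but has 10·11/2 = 55 parameters for at most 60 participants. Simulated with a t cut-off on 58 df (2,000 runs), its size was 8 to 9% whatever the scan share, zero included. That is a small-sample problem and not a missing scan term.

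**A separate matter: pooling of visit variances.** Intercepts-only and compound symmetry use one variance for both visits. Suppose the scan term is present but variances are pooled:
- Day-90 SD 1.2 times the Day-28 SD: pooled variance (1 + 1.44)/2 = 1.22, size 3.0%.
- Day-90 SD 1/1.2 = 0.83 times: pooled variance (1 + 0.694)/2 = 0.847, size 7.1%.

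Without the scan term, intercepts only gives about 3.4, 4.3 and 5.3% at 1.2 times and about 7.8, 9.1 and 10.7% at 0.83 times, for p = 10, 30 and 50%. At p = 10% and 0.83 times, adding the scan term moves 7.8% only to 7.1%, so there most of the departure from 5% is due to pooling.

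**The case against.** The strongest reply is that the text permits a sound model. The unstructured sentence directly follows one about repeated measures within a participant, so it can be read as a matrix over all of that participant's records. The clause on clinical outcomes points to visits within participant. Both readings keep the scan variance, and the intercepts-only reading sets aside the plan's own unstructured sentence. This stands as far as it goes, but neither reading is stated for the lobe model. The full matrix brings its own small-sample error, and the fallback, read over the same records, does lose scan variance.

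A second reply is that large scan shares are unlikely. Both changes subtract the same baseline scan, so baseline error falls into the participant component. If the three scans have equal, independent technical error and nothing else differs by visit, then ss cannot exceed sp. So p ≤ 0.8 − p, that is p ≤ 40% under the split used here. Lasting differences in recovery lower it further. The breath hold is coached and scan settings are to be held constant across visits. This stands too: 50% is an extreme case.

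A reader might infer that the primary test is anti-conservative however it is fitted, or that its error rate is near 10%. The documents support neither. Several readings are unaffected by the missing term, the largest figures come mainly from variance pooling, and pooling can equally make the test conservative.

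**Conclusion.** The covariance of the sub-study's primary model is under-specified. Three ways of fitting it (intercepts only, unstructured visits within lobe, compound symmetry over all of a participant's records) can leave out part of the shared scan variance at Day 28. With equal visit variances, the nominal 5% test has size of about 5.5 to 8.0% for scan shares of 10 to 50% (compound symmetry 5.0 to 7.6%). At shares of 20% or less, on the scale of a participant's mean change, the excess is at most about 1 point.

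These figures rest on five lobes, the assumed variance split and complete data. The documents give no variance components, so the actual size is unknown. If Day-28 and Day-90 variances differ, intercepts-only and compound symmetry can err in either direction.

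The consequence is modest: this is an exploratory, voluntary sub-study of at most 60 participants. The master protocol was not available, so any general analysis conventions there could not be checked. The point is worth settling before analysis because it decides how the one primary test is computed. It does not show that the power table is wrong.

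**What to change.** Make the per-scan composite the primary outcome, with one percent BV5 change per participant and visit. Use fixed effects for arm, visit and arm by visit, an unstructured 2x2 covariance over Day 28 and Day 90 within participant, and a named small-sample df method such as Kenward-Roger.

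Fix the composite formula in advance. The simple mean of lobar values gives the same Day-28 estimate as the lobe model when data are complete. A volume-weighted whole-lung value is closer to the percent-of-total measure under Criteria for Evaluation, but is a slightly different estimand.

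If lobe rows are kept, add a participant-by-visit random effect with visit-specific variances, define the lobe intercept as lobe within participant, and keep the participant-by-visit term in the fallback.

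The cost is analysis-plan wording and one decision on the formula. No new data or participants are needed. With complete data and 58 df the recommended Day-28 test is the t-test behind the power table. The downside is a slightly larger Day-28 standard error in some cases, and commitment to one composite.

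### The lobe-level primary model for percent BV5 does not say which records its unstructured covariance matrix spans and names no small-sample correction, so the Day 28 test's false-positive rate runs from about 5% to about 10% depending on the reading

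*Combined protocol and SAP*

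**What the plan says.** All references are to section 3 of the sub-protocol, CT Imaging Substudy.

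- **Statistical Analyses.** The primary model regresses the Day 28 and Day 90 changes in percent BV5 on arm, visit, arm by visit, and lobe, with random intercepts for lobe and participant. The primary hypothesis is tested on the Day 28 treatment coefficient. The covariance statement is one sentence: "An unstructured variance-covariance matrix will be assumed". Compound symmetry is to be considered only if the fit does not converge.
- **The same section** offers a participant-level route: if needed, "a per-scan composite from across all lobes may be formed". It does not define what makes this necessary or how lobes are combined.
- **Sub Study Design.** "The CT imaging sub-study is designed to compare up to 60 total patients", so 60 is a ceiling.
- **Sample Size and Power.** "These calculations are based on a two-sided t-test comparing the change from baseline between the acebilustat and placebo arms". This uses one value per participant. Also: "In all calculations, a total sample size of 60 and a Type I error of 0.05 were assumed".

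The substudy text does not give the dimension of the matrix, REML or ML, the denominator degrees of freedom, or a small-sample adjustment.

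**The concern.** A lobe-level analysis produces several records per participant per scan. If the unstructured matrix is taken over all of them, it has many parameters relative to at most 60 participants. The usual model-based standard error treats the estimated matrix as if it were known, so it is too small. A degrees-of-freedom rule applied afterwards does not cure this, because the fault lies in the standard error itself.

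Under that reading, the Day 28 test would not hold the 0.05 Type I error assumed in the power section, and its confidence interval would be too narrow. Under other readings the problem is small or absent. At stake is whether the error rate of the primary imaging hypothesis is fixed by the plan or by whoever writes the model code.

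**Working it through.** **Inputs from the plan.** N = 60, two-sided alpha = 0.05, allocations 30/30, 35/25 and 40/20 (Sample Size and Power); two post-baseline visits, the fixed effects, random intercepts and covariance wording (Statistical Analyses).

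**Assumptions.** Five lobes (the plan gives no number), complete data, and the variance components stated below.

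**1. The plan's own figure.** Power uses the noncentral t with 58 df and noncentrality δ/√(1/n₁ + 1/n₂).
- 30/30, δ = 0.8: 0.8/√(2/30) = 3.098, power 0.861 (plan 0.86).
- 40/20, δ = 0.8: 0.8/√(0.075) = 2.921, power 0.819 (plan 0.82).

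All 12 cells reproduce to rounding. The table is correct for a participant-level t-test, which is not the lobe-level model.

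**2. Size of the matrix under the widest reading.** 5 lobes x 2 visits = 10 records per participant, and 10 x 11/2 = 55 covariance parameters.

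**3. Analytic check of the widest reading.** Treatment enters through 2 of 10 dimensions (one per visit), so the fit in effect adjusts for the other k = 8 contrasts using m = 58 residual df.
- Ratio of model-based to true variance: (50/58) x (49/57) = 0.741.
- Ratio of standard errors: √0.741 = 0.861, that is, about 14% too small.
- Rejection rate with a 1.96 cut-off: 2·P(t₅₀ > 1.96 x 0.861) = 9.8%. With the t(58) cut-off of 2.002: 9.1%.

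**4. Simulation of the widest reading** (no treatment effect, REML, 10 x 10 unstructured).

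| Allocation | t(58) | z |
|---|---|---|
| 30/30 (30,000 replicates) | 9.3% | 10.0% |
| 40/20 (30,000 replicates) | 9.1% | 9.7% |
| 30/30, three true covariance matrices (10,000 each) | 8.8-9.4% | 9.4-10.0% |

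With fewer participants, using a t cut-off and z respectively, the rates are 10.2% and 11.2% at 24/24, and 12.5% and 13.6% at 20/20.

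With participant/scan/lobe/residual components of 0.4/0.2/0.2/0.2 at 30/30, the mean model SE was 0.198 against an actual 0.230 (ratio 0.861, as in step 3).

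**5. Narrower readings at 30/30** (1,000 replicates each; Monte Carlo standard error near 5% is √(0.05 x 0.95/1000) = 0.7 points). Each range runs from t(58) to z.

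| Reading | No shared scan effect | Shared scan effect present |
|---|---|---|
| 2 x 2 participant-by-visit matrix plus lobe intercept | 5.1-5.9% | 5.1-5.6% |
| 2 x 2 residual matrix within lobe | 5.6-5.9% | 6.7-7.3% |
| Compound-symmetry fallback | 5.2-5.7% | 6.5-7.0% |

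**6. Repairs at 30/30.**
- Wide matrix with Kenward-Roger: 5.7% (6,000 replicates), and 5.4% and 5.5% in separate runs. Mean SE was 0.223 against 0.197 uncorrected, and 0.223/0.197 = 1.13.
- Wide matrix with Satterthwaite degrees of freedom only: 9.3%.
- Per-scan composite with a 2 x 2 visit matrix: 5.0% with t(58); with z, 2·P(t₅₈ > 1.96) = 5.5%.

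**7. Precision of the composite** under the same components. Its variance is 0.4 + 0.2 + 0.2/5 + 0.2/5 = 0.68, so its SE is √(0.68 x 2/30) = 0.213, about 7% below the 0.230 actually delivered by the wide lobe-level fit.

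**The case against.** The strongest reply is that the widest reading is not the only natural one. A full 10 x 10 matrix already absorbs the participant and lobe intercepts and would make the plan's preceding sentence redundant. Reading the matrix as covering the two visits leaves those intercepts something to do. If intercepts and full matrix were fitted together, the redundancy could prevent convergence and trigger compound symmetry. The endpoint also sits under a heading that calls the efficacy endpoints exploratory, in a voluntary substudy, and analysis conventions in the master protocol, which is not among the documents, cannot be ruled out.

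Much of this stands. A reader might infer that the primary test simply has a 9-10% error rate, but the documents do not support that: the figure needs a matrix dimension the plan never states. A reader might also infer that missing scans make matters worse. The runs with fewer participants show the effect of smaller N, but all used complete data, so the effect of missing visits was not computed.

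What does not stand is that the ambiguity is harmless. A single random intercept has a scalar variance, for which unstructured has no meaning, so the sentence must refer to some set of records, and the wide set is an admissible choice. The fallback applies only on non-convergence and is itself mildly anti-conservative if lobes in a scan share an unmodelled effect. Although headed exploratory, the endpoint is called primary within the substudy, is powered at 0.05 and carries a formal hypothesis test.

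**Conclusion.** The point holds as an under-specified primary analysis whose error rate depends on an unstated choice. At 60 participants, five lobes and complete data, the nominal 5% Day 28 test rejects a true null about 9% (t) to 10% (z) of the time under the widest reading. Under the narrower readings the rate is about 5-6%, rising to 6.5-7.3% for the within-lobe matrix or compound symmetry when a shared scan effect is left out of the model.

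The 9-10% agrees between simulation and the analytic check and was stable across the covariance patterns tried. The narrower-reading figures carry more simulation error. The exploratory label limits the consequence: this should be corrected, but it does not bear on the main trial's conclusions. No reading of the lobe-level model was shown to control error better than the composite.

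**What to change.** **Preferred.** In Statistical Analyses, make the per-scan composite the primary level and state how lobes are combined. Fit arm, visit and arm by visit, with a 2 x 2 unstructured matrix over Day 28 and Day 90 within participant, and use t-based inference. Keep the lobe-level model as secondary. This holds about 5% and puts the primary analysis on the same footing as the power calculation.

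**If the lobe-level model stays primary.** State which records the matrix spans, and require REML with Kenward-Roger standard errors and degrees of freedom for the Day 28 test and interval. Satterthwaite degrees of freedom alone are not enough under the wide reading.

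**Cost.** A short change to the SAP text and a standard software option; no change to data collection. Under the wide reading, Kenward-Roger widens the lobe-level interval by about 13%, which corrects its width. The composite's 7% precision advantage was found with equal variances and correlations across lobes and may differ if lobes are unequal.
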